11.2.2 Listing of Adverse Event

Listings of all serious adverse events (from the time the subject signed the study-specific informed consent until the end of the study), treatment-emergent serious adverse events, treatment-emergent adverse events leading to death, treatment-emergent adverse events leading to discontinuation of study drug, treatment-emergent adverse events leading to study drug interruptions, treatment-emergent adverse events leading to RBV dose modifications, and treatment-emergent adverse events of special interest will be provided.

11.3 Analysis of Laboratory Data

Data collected from central and local laboratories, including additional lab testing due to all SAE will be used in all analysis.

11.3.1 Variables and Criteria Defining Abnormality

Hematology variables include: hematocrit, hemoglobin, red blood cell (RBC) count, white blood cell (WBC) count, neutrophils, bands, lymphocytes, monocytes, basophils, eosinophils, platelet count, absolute neutrophil count (ANC), reticulocyte count, PT/INR, and activated partial thromboplastin time (aPTT).

Chemistry variables include: blood urea nitrogen (BUN), creatinine, total bilirubin, direct and indirect bilirubin, serum glutamic pyruvic transaminase (SGPT/ALT), serum glutamic oxaloacetic transaminase (SGOT/AST), alkaline phosphatase, sodium, potassium, calcium, inorganic phosphorus, uric acid, cholesterol, total protein, glucose, triglycerides, albumin, chloride, bicarbonate, magnesium, gamma glutamyl transferase (GGT), total insulin, creatinine clearance (Cockcroft-Gault calculation), calculation of estimated glomerular filtration rate (eGFR) using the modification of diet in renal disease (MDRD)

equation as defined below, alpha2-macroglobulin, haptoglobin, apolipoprotein A1, and alpha fetoprotein.

Urinalysis variables include: specific gravity, ketones, pH, protein, blood, glucose, urobilinogen, bilirubin, leukocyte esterase, albumin, and microscopic (reflexly performed if other variables are abnormal).

Additional variable is total insulin.

The following equation will be used to calculate eGFR by MDRD, where serum creatinine is measured in mg/dL and age is measured in years:

$$\text{GFR (mL/min/1.73 m}^2\text{)} = 175 \times \text{Serum Creatinine}^{-1.154} \times \text{Age}^{-0.203} \times 1.212 \text{ (if Black)} \\ \times 0.742 \text{ (if Female).}$$

The Criteria for Potentially Clinically Significant (PCS) Laboratory Findings are described in [Table 8](#) and [Table 9](#).

Table 8. Criteria for Potentially Clinically Significant Hematology Values

Test/Units	Very Low (VL)	Very High (VH)
Hemoglobin		
(mmol/L)	< 4.9	
(g/dL)	< 8.0	
(g/L)	< 80	
Platelets Count		
(cells/mm ³)	< 50,000	
(cells/L)	< 50 × 10 ⁹	
White Blood Cell Count		
(cells/mm ³)	< 2000	> 20,000
(cells/L)	< 2.0 × 10 ⁹	> 20 × 10 ⁹
Absolute Neutrophil Count		
(cells/mm ³)	< 1000	
(cells/L)	< 1 × 10 ⁹	
Lymphocyte Count		
(cells/mm ³)	< 500	
(cells/L)	< 0.5 × 10 ⁹	
Eosinophil Count		
(cells/mm ³)		> 5000
(cells/L)		> 5 × 10 ⁹
aPTT		> 2 × ULN
International Normalized Ratio		> 2 × ULN

Note: A post-baseline value must be more extreme than the baseline value to be considered a PCS finding.

Table 9. Criteria for Potentially Clinically Significant Chemistry Values

Test/Units	Very Low (VL)	Very High (VH)
ALT/SGPT		$> 5 \times \text{ULN}$ and $\geq 2 \times \text{baseline}$
AST/SGOT		$> 5 \times \text{ULN}$ and $\geq 2 \times \text{baseline}$
Alkaline Phosphatase		$> 1.5 \times \text{ULN}$
Total Bilirubin (mg/dL)		$\geq 2.0 \times \text{ULN}$
Creatinine		
(mcmol/L)		≥ 132.605
(mg/dL)		≥ 1.5
Creatinine Clearance (mL/min)	< 50	
BUN		$> 5 \times \text{ULN}$
Uric Acid		
(mcmol/L)		> 713.817
(mg/dL)		> 12.0
Phosphate		
(mmol/L)	< 0.6	
(mg/dL)	< 2.0	
Calcium, Serum		
(mmol/L)	< 1.75	> 3.1
(mg/dL)	< 7.0	> 12.5
Sodium (mmol/L)	< 130	> 155
Potassium (mmol/L)	< 3.0	> 6.0
Magnesium		
(mmol/L)	< 0.4	> 1.23
(mg/dL)	< 0.9	> 3.0
Glucose		
(mmol/L)	< 2.2	> 13.9
(mg/dL)	< 40	> 250
Albumin		
(g/L)	< 20	
(g/dL)	< 2	

Table 9. Criteria for Potentially Clinically Significant Chemistry Values (Continued)

Test/Units	Very Low (VL)	Very High (VH)
Protein		
(g/L)	< 50	
(g/dL)	< 5.0	
Cholesterol		
(mmol/L)		> 10.34
(mg/dL)		> 400
Triglycerides		
(mmol/L)		> 5.7
(mg/dL)		> 500

Note: A post-baseline value must be more extreme than the baseline value to be considered a PCS finding.

11.3.2 Statistical Methods

Clinical laboratory tests will be summarized at each visit during the Treatment Period. The baseline value will be the last measurement on or before the day of the first dose of study drug. This same baseline value will be used for all change from baseline tables in the Treatment Period and Post-Treatment Periods.

Mean changes from baseline to each post-baseline visit, including applicable post treatment visits, will be summarized for each protocol-specified laboratory parameter with the baseline mean, visit mean, change from baseline mean, standard deviation, and median.

Laboratory data values will be categorized as low, normal, or high based on normal ranges of the laboratory used in this study. Shift tables from baseline to minimum value, maximum value, and final values during the Treatment Period (Study Drug End Day \leq 2) will be created. The shift tables will cross tabulate the frequency of subjects with baseline values below/within/above the normal range versus minimum/maximum/final values below/within/above the normal range.

The number and percentage of subjects with post-baseline values during the Treatment Periods meeting the specified criteria for Potentially Clinically Significant (PCS) laboratory values (defined in [Table 8](#) and [Table 9](#)) will be summarized. A post-baseline value must be more extreme than the baseline value to be considered a PCS finding. A separate listing will be provided that presents all lab values for the subjects meeting PCS criteria during treatment.

For hemoglobin and the liver function tests (LFTs) of alkaline phosphatase and total bilirubin, the number and percentage of subjects with a maximum Common Terminology Criteria for Adverse Events (CTCAE) Grade of 1, 2, 3, or 4 (see definitions in [Table 10](#)) at any post-baseline visit (regardless of the baseline value) through the end of treatment (i.e., Final Treatment Value) will be summarized. All LFT tables will include summary rows for the number and percentage of subjects with at least Grade 2 and at least Grade 3 laboratory abnormalities. The hemoglobin table will include a summary row for the number and percentage of subjects with at least a Grade 2 laboratory abnormality.

For the liver function tests (LFTs) of ALT and AST, the number and percentage of subjects with a maximum Common Terminology Criteria for Adverse Events (CTCAE) Grade of 1, 2, 3, or 4 (see definitions in [Table 10](#)) at any post-nadir visit (regardless of the baseline value) through the end of treatment (i.e., Final Treatment Value) will be summarized. Note, for these analyses, the nadir is used for reference instead of baseline. Both ALT and AST tables will include summary rows for the number and percentage of subjects with at least Grade 2 and at least Grade 3 laboratory abnormalities.

Accompanying listing of hemoglobin results will be provided for any subjects with at least Grade 2 hemoglobin abnormalities. Accompanying listings of all ALT, AST, total, indirect and direct bilirubin, and alkaline phosphatase will be created for any subject who had at least a Grade 3 ALT, AST, alkaline phosphatase, or total bilirubin. A listing of the hematology results will be provided for subjects with hemoglobin abnormalities.

Table 10. Definitions of CTCAE Grades 1, 2, 3, and 4

Test	Grade 1	Grade 2	Grade 3	Grade 4
ALT/SGPT	> ULN – 3 × ULN	> 3 – 5 × ULN	> 5 – 20 × ULN	> 20 × ULN
AST/SGOT	> ULN – 3 × ULN	> 3 – 5 × ULN	> 5 – 20 × ULN	> 20 × ULN
Alkaline Phosphatase	> ULN – 2.5 × ULN	> 2.5 – 5 × ULN	> 5 – 20 × ULN	> 20 × ULN
Total Bilirubin	> ULN – 1.5 × ULN	> 1.5 – 3 × ULN	> 3 – 10 × ULN	> 10 × ULN
Hemoglobin Decreased	< LLN – 100 g/L	< 100 – 80 g/L	< 80 – 65 g/L	< 65 g/L

The number and percentage of subjects meeting the following criteria will be summarized:

- ALT $\geq 3 \times$ ULN and total bilirubin value $\geq 2 \times$ ULN;
- ALT $> 5 \times$ ULN (equivalent to Grade 3 or higher) and total bilirubin value $< 2 \times$ ULN.

A subject or event will be counted if the post-nadir laboratory values meet the above criteria regardless of the baseline laboratory value (i.e., the post nadir laboratory value does not need to be worse than the baseline laboratory value). The maximum ratio relative to the ULN will be used to determine if subjects meet the criteria listed above.

For subjects meeting the ALT $\geq 3 \times$ ULN and total bilirubin value $\geq 2 \times$ ULN criterion during the Treatment Period, a corresponding listing of all ALT, AST, alkaline phosphatase, and total, direct, and indirect bilirubin values will be provided.

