**Table 5. Treatment Regimen and Duration**

Subject Population	Treatment Regimen*	Treatment Duration
Genotype 1a, without cirrhosis	ABT-450/r/ABT-267 + ABT-333 + ribavirin	12 weeks
Genotype 1a, with cirrhosis	ABT-450/r/ABT-267 + ABT-333 + ribavirin	24 weeks**
Genotype 1b, without cirrhosis	ABT-450/r/ABT-267 + ABT-333	12 weeks
Genotype 1b, with cirrhosis	ABT-450/r/ABT-267 + ABT-333 + ribavirin	12 weeks

\* Follow the genotype 1a dosing recommendations in patients with an unknown genotype 1 subtype or with mixed genotype 1 infection.

\*\* Treatment for 12 weeks may be considered in some patients where consistent with the approved local label.

The site will enter subject's genotype (1b/Non-1b), fibrosis stage and prior IFN-based treatment information in the IRT system in order to assign subject's treatment regimen as described in [Table 5](#).

ABT-450/r/ABT-267, ABT-333 and RBV (if applicable) will be administered as described in [Section 5.5.1](#). Subjects will receive instructions about the study drugs and the dosing schedule at the Day 1 Visit. The study drugs will be dispensed at the visits indicated in [Table 7](#).

All subjects will continue to return to the site on an outpatient basis through Week 12 or Week 24 depending on treatment assignment, following the study procedures identified in [Table 7](#). Subjects could also return to the site as an unscheduled study visit for additional safety visits if the investigator feels it is necessary. Sites should ensure that subjects adhere to the study visits. Sites should provide additional study drug for subjects who cannot complete their study visit per the visit schedule to ensure they do not run out of study drug prior to their next study visit. Compliance is critical to ensure adequate drug exposure.

Some of the Treatment Period study visits and visit activities (including but not limited to vital signs, clinical laboratory tests, and concomitant medication assessment) may be conducted in the home or non-hospital/clinic environment by qualified individuals at the

request of the Investigator, with approval from the Sponsor, and with the agreement of the subject.

Virologic failure criteria will be evaluated and applied by the investigator as detailed in Section 5.4.3.

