**Table 6. Medications Contraindicated for Use with the Study Drug Regimen**

For medications contraindicated with AbbVie's 3 DAA regimen, refer to the recommended prescribing information section of the approved local product labels in countries where the regimen contained in this study (i.e., ABT-450/r/ABT-267 and ABT-333) has received marketing authorization. If locally approved labels are not available, refer to the following Contraindicated Medication list:

Alfuzosin	Ethinyl estradiol-containing medications	Pimozide
Astemizole	Fusidic Acid	Rifampin
Carbamazepine	Gemfibrozil	Salmeterol
Cisparide	Lovastatin	Sildenafil*
Dihydroergotamine	Methylergonovine	Simvastatin
Efavirenz	Midazolam (oral)	St. John's Wort
Ergotamine	Phenobarbital	Terfenadine
Ergonovine	Phenytoin	Triazolam

\* When used for the treatment of pulmonary arterial hypertension.

Note: Not all medications contraindicated with ritonavir, ribavirin, and 3DAA regimen are listed above. Refer to the most current package inserts or product labeling of ritonavir and ribavirin for a complete list of contraindicated medications.

4. Use of known moderate or strong inducers of cytochrome P450 3A (CYP3A) or strong inducers of cytochrome P450 2C8 (CYP2C8) or strong inhibitors of CYP2C8 within 2 weeks of the respective medication/supplement, prior to initial dose of study drug.
5. Clinically significant abnormalities or co-morbidities, other than HCV infection that in the opinion of the investigator make the subject an unsuitable candidate for this study or drug regimen.
6. Current enrollment in another interventional clinical study, previous enrollment in this study, prior or current use of any investigational or commercially available anti-HCV agents other than IFNs or RBV (including previous exposure to ABT-450, ABT-267 or ABT-333), or receipt of any investigational product within 6 weeks prior to study drug administration.
7. History of solid organ transplant.
8. Screening laboratory analyses showing any of the following abnormal laboratory results:
  - Creatinine Clearance (CrCl) < 30 mL/min as estimated by the Cockcroft-Gault equation:
$$\text{CrCl} = \frac{[(140 - \text{Age}) \times \text{Mass (in kg)} \times (0.85 \text{ if female})]}{[72 \times \text{Serum creatinine (in mg/dL)}]}$$
  - Albumin < 2.8 g/dL
  - Hemoglobin < LLN
  - Platelets < 25,000 cells per mm^3
  - Total bilirubin > 3.0 mg/dL

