6.2 Analysis Windows

For efficacy analyses of HCV RNA and resistance, the time windows specified in [Table 2](#) and [Table 3](#) describe how efficacy data are assigned to protocol-specified time points during the Treatment and PT Periods, respectively. All time points and corresponding time windows are defined based on the blood sample collection date.

For analyses of health-related quality of life (QoL) PROs collected throughout the study, the time windows specified in [Table 4](#) will be used.

For laboratory data and vital signs, the time windows specified in [Table 5](#) and [Table 6](#) describe how data are assigned to protocol specified time points during the Treatment and PT Periods, respectively.

If more than one assessment is included in a time window, the assessment closest to the nominal time will be used. If there are two observations equally distant to the nominal time, the latest one will be used in analyses. The only exception to this is for the SVR windows (e.g., SVR₄, SVR₁₂, and SVR₂₄); for these windows, the last value in the window will be used.

If multiple measurements are made on the same day for a safety laboratory parameter or a vital sign parameter, the average of the values will be used in analyses. For summaries of shifts from baseline and potentially significant values, multiple values on the same day will not be averaged; all values will be considered for these analyses.

Table 2. Analysis Time Windows for HCV RNA and Resistance Endpoints (Treatment Period)

Scheduled Visit	Nominal Day (Study Day)	Time Window (Study Day Range)
Day 1/Baseline ^a	1a	≤ 1 ^a
Week 2	14	2 to 21
Week 4	28	22 to 56
Week 12	84	57 to 126
Week 24 ^b	168	127 to 182
Final Treatment Visit ^c		2 to ≤ 2 days after last dose of study drug

a. Day of first dose of study drug.

b. Week 24 Visit is only applicable to subjects assigned to 24 weeks of treatment.

c. The last value within the window will be used to define the Final Treatment visit value.

Note: Data must also have Study Drug End Day ≤ 2 for all windows. The result closest to the scheduled time point will be used.

Table 3. Analysis Time Windows for HCV RNA and Resistance Endpoints (Post-Treatment Period)

Scheduled Visit^a	Nominal Day (Study Drug End Day)	Time Window (Study Drug End Day Range)
Post-Treatment Week 4	28	3 to 56
Post-Treatment Week 12	84	57 to 126
Post-Treatment Week 24	168	127 to 266
Post-Treatment Week 52	364	267 to 546
Post-Treatment Week 104	728	547 to 910

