7.1 Demographic and Baseline Characteristics

Demographics include age, weight, height and BMI as continuous variables, and sex, race, ethnicity, age category (< 55 years or ≥ 55 years] and [< 65 or ≥ 65 years]), birth year (< 1945 , 1945 to 1965, > 1965), country, and BMI category (< 30 kg/m² or ≥ 30 kg/m²).

Baseline characteristics will include: HCV genotype 1 subtype (1a, 1b, 1-other), IL28B genotype ([CC, CT, or TT] and [CC or non CC]), prior treatment history (treatment-naïve [IFN-eligible, IFN-ineligible] or IFN-based treatment-experienced [null responder, partial responder, relapser, prior relapse/breakthrough, prior nonresponder, IFN-intolerant and IFN experienced-other]), baseline HCV RNA levels ([continuous (use log₁₀ HCV RNA)])

and [$< 800,000$ IU/mL or $\geq 800,000$ IU/mL]), baseline HOMA-IR (< 3 or ≥ 3 $\text{mU} \times \text{mmol/L}^2$), baseline fibrosis stage (F0 – F1, F2, F3, F4), baseline Child-Pugh score (non-cirrhotic, 5, 6, or > 6), baseline FibroTest score (continuous and [< 0.49 , $0.49 - 0.58$, $0.59 - 0.74$, ≥ 0.75]), baseline albumin (continuous), baseline albumin (< 35 , ≥ 35 g/L), baseline creatinine clearance (continuous; < 30 mL/min, $\geq 30 - 49$ mL/min, $\geq 50 - 89$ mL/min, ≥ 90 mL/min), baseline eGFR by MDRD (continuous; < 30 , $30 - 59$, $60 - 89$, ≥ 90 mL/min/1.73 m²; < 60 or ≥ 60 mL/min/1.73 m²), baseline platelet count (continuous; $< 90 \times 10^9/\text{L}$, $\geq 90 \times 10^9/\text{L}$; $< 50 \times 10^9/\text{L}$, $\geq 50 \times 10^9/\text{L}$; $< 100 \times 10^9/\text{L}$, $\geq 100 \times 10^9/\text{L}$; $< 150 \times 10^9/\text{L}$, $\geq 150 \times 10^9/\text{L}$), baseline alpha fetoprotein (continuous, and < 20 ng/mL, ≥ 20 ng/mL), tobacco (user, ex-user, or non-user) and alcohol (drinker, ex-drinker, or non-drinker) use status, history of diabetes, history of depression or bipolar disorder, history of bleeding disorders, AST to platelet ratio index (APRI) (continuous; ≤ 2.0 or > 2.0), and Fibrosis-4 score (FIB-4) (continuous; ≤ 3.25 , > 3.25).

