8.0 Patient Disposition

The number of subjects for each of the following categories will be summarized overall and by each investigator on the safety population.

- Subjects who took at least one dose of study drug;
- Subjects who completed study drug;
- Subjects who discontinued from study drug;
- Subjects who completed the study;
- Subjects ongoing in the Post-Treatment Period at the time of the interim analysis;
- Subjects who discontinued from the study.

The number and percentage of subjects who discontinued study drug will be summarized by reason (all reasons) and by primary reason (per eCRF). Similar summaries will be provided for discontinuations from the study.

The number and percentage of subjects will be summarized for:

- Subjects with interruptions of all study drugs for toxicity management;
- Subjects with any RBV dose modification;
 - Subjects with RBV dose modification due to decrease in hemoglobin;
 - Subjects with RBV dose modification due to decrease in creatinine clearance;
 - Subjects with RBV dose modification due to weight change;
 - Subjects with RBV dose modification due to other reasons;
- Subjects with any RBV dose modification to 0 mg (i.e., RBV interruptions).

Reasons for study drug interruptions and RBV dose modifications will be presented in the CSR listings.

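### PCS laboratory counts for creatinine clearance and platelets pool new crossings of the limit with trivial worsening in subjects who entered beyond it; report them by baseline status

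*SAP*

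**What the plan says.** - **Counting rule.** SAP 11.3.2 summarizes the number and percentage of subjects whose on-treatment values meet the limits in Tables 8 and 9, with one figure per parameter. The condition "A post-baseline value must be more extreme than the baseline value to be considered a PCS finding" sets no minimum amount. Only ALT and AST carry a further requirement (at least 2 × baseline).
- **Repeat values.** SAP 6.2 adds: "For summaries of shifts from baseline and potentially significant values, multiple values on the same day will not be averaged". Every value can therefore trigger a flag.
- **Limits.** Creatinine clearance below 50 mL/min (Table 9) and platelets below 50,000/mm³ (Table 8).
- **Entry.** Protocol 5.2.2, criterion 8, excludes creatinine clearance only below 30 mL/min. For platelets the exclusion is "Platelets < 25,000 cells per mm"³. Protocol 5.5.1 provides a reduced ribavirin dose for clearance of 30 to below 50.
- **Baseline groups.** SAP 7.1 tabulates baseline clearance with a 30–49 category, and platelets below versus at least 50 × 10⁹/L. SAP 10.5 uses the 50 mL/min cut, and in subjects with cirrhosis the 50 × 10⁹/L cut, for SVR12 subgroups. The PCS table uses neither.

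**The concern.** A PCS percentage is normally read as the proportion of subjects who developed a notable abnormality on treatment. For a subject who starts beyond the limit, the limit does no work: any later value below baseline is automatically beyond it. The rule then reduces to whether any on-treatment value was lower than baseline, which measurement noise alone usually satisfies. That subject and one who falls from 95 to 49 mL/min add equally to the same count.

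The plan treats similar problems differently elsewhere. ALT and AST must double. In Table 11, blood pressure, heart rate and temperature need a limit and a minimum change, and weight needs a minimum percentage change. Protocol 6.7.6 sets its renal action level by baseline: to below 50 from at least 50, or to below 30 from below 50. At stake is the reading of the renal and platelet safety rows, not any efficacy result.

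**Working it through.** The plan states no figure on this point, so there is nothing to reproduce. The check compares the limits, then asks how often a stable subject is flagged.

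**1. Overlap of entry and PCS ranges**

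| Parameter | Entry allowed | PCS | Overlap |
|---|---|---|---|
| Creatinine clearance | ≥ 30 mL/min | < 50 | 30 to < 50 |
| Platelets | ≥ 25,000/mm³ | < 50,000 | 25,000 to < 50,000 |
| Hemoglobin | ≥ LLN | < 8.0 g/dL | none expected |
| Albumin | ≥ 2.8 g/dL | < 2 g/dL | none |
| Total bilirubin | ≤ 3.0 mg/dL | ≥ 2 × ULN | only if ULN < 3.0/2 = 1.5 mg/dL; ULN not given |

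Creatinine (PCS ≥ 1.5 mg/dL) has no entry limit of its own but enters through Cockcroft-Gault. As an illustration, a man aged 70 weighing 70 kg with creatinine 1.5 mg/dL has clearance (140 − 70) × 70 / (72 × 1.5) = 45.4 mL/min. He is eligible and is beyond both PCS limits at baseline.

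**2. Draws.** Protocol Table 7 schedules K = 3 on-treatment panels for 12-week subjects (Weeks 2, 4, 12) and K = 4 for 24-week subjects (Weeks 2, 4, 12, 24).

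**3. Chance flag rate, stable subject.** If baseline and K later values are exchangeable without ties, baseline is the lowest with probability 1/(K + 1). So P(at least one worse value) = K/(K + 1):
- K = 3: 3/4 = 75%
- K = 4: 4/5 = 80%

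**4. Regression to the mean.** Subjects picked for a low measured baseline tend to read higher later, which lowers these rates. A simulation with no true change used assumed distributions (clearance mean 100, SD 28 mL/min; platelets mean 140, SD 55 × 10⁹/L). It gave these flag rates among subjects with baseline beyond the limit:

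| Within-subject CV | Clearance K=3 | K=4 | Platelets K=3 | K=4 |
|---|---|---|---|---|
| 5% | 69% | 75% | 72% | 77% |
| 8% | 65% | 71% | 70% | 75% |
| 12% | 60% | 65% | 67% | 72% |

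A wider set was also run. For clearance it used mean (SD) 100 (30), 95 (35) or 80 (25), CV 3–15%, and creatinine unrounded or rounded to 0.01 or 0.1 mg/dL. This gave 48–73% (K = 3) and 54–78% (K = 4). For platelets it used mean (SD) 130 (60), 180 (70) or 100 (45), CV 5–20%, rounded to 1. This gave 57–64% and 63–69%. Overall this is roughly 50–75%. Unscheduled and same-day repeat values are not modelled and would raise the rates.

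**5. Noise on the other side of the limit.** With no true change and K = 3, CV 3–15%, the share of subjects with baseline clearance ≥ 50 who show at least one value below 50 is 0.6–3.6% (100, SD 30), 0.9–5.2% (95, SD 35) and 1.4–8.5% (80, SD 25).

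**6. Count of chance flags.** This equals N × p × r, where p is the proportion entering beyond the limit and r the rate from step 4. The documents do not give p. With N = 1650, p = 1% and r = 0.50 give 1650 × 0.01 × 0.50 ≈ 8, while p = 5% and r = 0.75 give 1650 × 0.05 × 0.75 ≈ 62. The assumed clearance distributions above themselves put about 3–11% below 50. The spread shows that p governs the answer and is unknown.

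**7. Other planned outputs.** Shift tables use the normal range, not 50 mL/min or 50,000. CTCAE tables cover hemoglobin, alkaline phosphatase, bilirubin, ALT and AST. SAP 8.0 counts "Subjects with RBV dose modification due to decrease in creatinine clearance". That is not split by trigger level, and it cannot include the group "Genotype 1b, without cirrhosis", which receives no ribavirin under Protocol Table 5.

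**The case against.** The strongest reply is that this is table layout, not error. The rule is explicit, the study has one arm, and no test or decision uses the count. Requiring a value worse than baseline is already an adjustment for subjects abnormal at entry. The information is also planned: every new crossing is by definition a PCS flag, the listing shows all laboratory values for flagged subjects, and SAP 7.1 supplies the denominators. Protocol 8.1.6 permits additional analyses. All of this is correct and keeps the importance low. It does not remove the point, because the listing holds values without counting them and the permission in 8.1.6 does not specify this split.

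A second reply is that splitting does not isolate real decline. That also stands. A reader might take a within-limit row as true deterioration, but step 5 shows that noise near the limit contributes there too.

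A third reply concerns Protocol 6.7.6. A reader might infer that any single value below 30 mL/min would reproduce its trigger. It would not, because 6.7.6 requires the decrease to be confirmed, and it is a management rule rather than a rule for tables.

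Finally, entry beyond the limit is explicit for clearance, which has its own ribavirin dose. For platelets it follows from the exclusion limit and the SAP baseline category.

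**Conclusion.** The point holds as a cheap improvement of minor importance. The overlap and the any-worsening rule are facts of the text. The 75% and 80% figures need only stable, exchangeable values without ties. The range of roughly 50–75% rests on assumed distributions, variability and rounding. The pooled clearance and platelet percentages therefore partly reflect who was enrolled.

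Two stronger readings are not supported. A reader might infer that most of the pooled count is noise. The documents give neither the number entering beyond the limit nor the rate of real declines, so no share can be stated. A reader might also infer that Tables 8 and 9 are affected throughout. ALT and AST need a doubling, hemoglobin and albumin are protected by the entry limits, and bilirubin depends on an unstated ULN. For the remaining parameters nothing shows how many subjects, if any, enter beyond the limit, although creatinine is tied to clearance.

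**What to change.** Keep every PCS limit and the more-extreme-than-baseline rule. In SAP 11.3.2, report the PCS counts for creatinine clearance, platelets and creatinine separately for subjects within and beyond the limit at baseline, each with its own denominator. Cuts at 50 mL/min and 50 × 10⁹/L already follow from SAP 7.1 and 10.5; creatinine needs a baseline flag at 1.5 mg/dL. A footnote should say that the within-limit row shows new crossings, including some noise near the limit.

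Optionally, for baseline clearance below 50, add a count of confirmed values below 30 mL/min, in line with Protocol 6.7.6, with confirmation defined in the SAP.

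The cost is a few extra rows from data already collected, some with small denominators. No current flag is lost.
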